### *DMPA acceptors*

Family planning clients provide the basis for assessment of LHW and LHV service provision. Thus, the eligibility criteria for family planning clients of LHWs and LHVs are:

- Women who select DMPA as their contraceptive method for the first-time or after more than a six-month hiatus from the method;
- Women of reproductive age (18 to 49) who can legally consent to receive reproductive health services and participate in research studies in the Pakistani context;
- Women who consent to provision of DMPA services from LHWs or LHVs trained for the RCT;
- Women who provide consent to be observed and interviewed by independent data collectors during the trial.

### Sample size

We require a minimum of 342 DMPA clients randomized to receive care from either the LHV or an LHW (1:1 allocation) for 90% power and 5% significance level to test the non-inferiority hypothesis that LHWs can screen potential DMPA clients for method initiation just as adequately as LHVs with a non-inferiority margin of 7.5%, assuming that both LHVs and LHWs perform at a 95% success rate. In Pakistan, there is usually at least one LHV assigned to a health facility and many more LHWs affiliated with and under the supervision of resident LHVs. Therefore, we will use a 3 to 1 ratio of LHWs to LHVs at each health facility in the trial. The three LHWs will be placed on rotation to cover a three-month enrollment and data collection period in the health facility. Rotations among the three LHWs will be based on their individual availability and schedules; not on their perceived competencies or the preference of facility staff.

In order to meet the desired sample size from LHWs and LHVs, we will select 10 health facilities that provide the most DMPA in Karachi and Thatta districts. These facilities will be distributed between rural and urban areas. For logistical reasons, we plan to obtain the full target sample size of 342 DMPA initiators from the urban health facilities to ensure that adequate analyses can be done with this group. We will recruit additional participants from rural facilities to help assess possible differences in performance between LHVs and LHWs in rural and urban areas. Although, we don't expect these differences to exist, the additional sample size will help us to assess whether differences may be likely to exist. If we can be comfortable that providers in rural and urban areas perform in similar manner, the overall sample size for the analysis may be pooled for an increase in power. Please note, however, that the additional sample size from rural areas will not be adequate for separate analyses by location or to assess rural and urban differences statistically. Rural facilities will likely provide a much lower number of DMPA acceptors in the three-month data collection period, but they will each be selected for their ability to enroll at least 20 new acceptors in that period of time. We will then expect to enroll approximately 100 DMPA acceptors from the rural facilities in the recruitment period for an overall total sample size of approximately 442 for this study.

Given the relationship between LHWs and LHVs within clinics, we plan to account for the correlations of participant outcomes within providers and providers within clinics in the analysis. We expect that some of these correlations would lead to decreases in power, others to lead to increases in power for within

clinic comparisons. Power calculations were not adjusted for these potential correlations as the net effect on power may be offset with each other.

Please note that the screening outcome is not affected by the injection technique used, so power calculations focus on the overall comparison between LHV and LHW on the primary outcome. Furthermore, comparisons regarding injection techniques will be considered exploratory.

### ***Study procedures***

#### **Data collection instruments**

FHI 360 Headquarters (HQ) staff will develop two survey questionnaires and three observation checklists for screening and counseling first-time DMPA acceptors. One questionnaire—an exit interview-- will be administered to DMPA clients, and the other, to LHWs and LHV four to six months after initiation of the trial. Interviews with LHWs will be conducted during one of their routine visits to the health facility for resupply and supervision. LHWs will also be asked to present their family planning records at that time to determine if they properly maintain their injection and re-injection log books. Questions specific to LHWs and to LHV will be arranged in separate sections of the instrument with appropriate skip patterns.

Three observation checklists will be developed for screening and counseling DMPA users. Independent observers will document screening and counseling procedures employed by LHWs and LHV on one checklist, while the other two checklists will document injection technique separately for DMPA IM and SP.

#### ***Questionnaires***

The questionnaire items in the client exit interview instrument will focus on the following domains:

- Sociodemographic characteristics
- Experiences using contraceptive methods
- Factors in her decision to use DMPA
- Interaction with and information provided by LHW/LHV about DMPA
- Satisfaction with her choice of DMPA as a contraceptive method (IM or SP)
- Satisfaction with LHW/LHV

Questionnaire items in the LHW/LHV interview instrument will focus on:

- Sociodemographic characteristics
- Knowledge of DMPA use and provision
- General experiences and satisfaction with providing DMPA services
- Reports of needlestick injuries
- Observations of LHW (re)-injection logs

### *Observation checklists*

The first checklist will adapt the 15 screening items from FHI 360's "Checklist for Screening Clients Who Want to Initiate DMPA" (Figure 2). It includes pregnancy checklist items that determine client eligibility for DMPA use in the absence of pregnancy tests. The pregnancy checklist has been endorsed by WHO, is a proven proxy for pregnancy tests and is indispensable in non-clinical settings. In addition, items that capture the presence or absence of counseling on DMPA use will be incorporated as a second part of this checklist instrument, such as:

- Discussion of advantages and disadvantages of DMPA use
- Danger signs of DMPA use
- Side effects and management of DMPA

The remaining two checklists will separately assess LHW and LHV injection technique for DMPA IM and SP. The content of the checklists will be adapted from instruments developed for previous task sharing studies of injectable contraception and from PATH's Sayana Press® training materials.

All three checklists will be modified to capture the information from the point of view of the observer. That is, RAs will be asked to: 1) record if the LHW/LHV uses a physical checklist during screening and counseling; 2) make note of the questions asked and the responses given for the items on the checklists; and 3) document LHW's/LHV's decision(s) in light of client responses.

### Pilot testing and recruitment procedures

Before the trial is initiated, we will pilot test not only the client exit interview instrument, but also procedures associated with recruitment, consent, randomization, blinded assessment and verification of DMPA eligibility by the independent, clinically-trained staff member. The client interview instrument will be pilot tested to ensure that 1) the items are understandable to DMPA clients, 2) they elicit the intended information, and 3) research assistants (RAs) acquire real-world practice in administering the interviews. Recent and continuing DMPA clients who may be known to Jhpiego's LHW and LHV trainees will be identified and asked to assist with pilot testing the instruments.

Pilot testing study procedures will familiarize RAs and health facility staff with the order and logic of randomization and blinding to reduce the occurrence of procedural errors that may compromise the quality and reliability of the findings.

The provider interview instrument will also be pilot tested to ensure that the intended information is gathered and that RAs acquire practice in its administration.

Since pilot testing is solely for providing practice to research staff and to improve the comprehensibility of our materials, data collection instruments will be destroyed by AKU after the necessary information has been obtained.

Observation checklists have already been vetted through use in previous studies. However, RAs will be thoroughly trained by AKU staff to accurately record their observations of screening, counseling and injection technique in a standardized manner. AKU staff will receive guidance and in-person technical

assistance from the FHI 360 Project Leader on data quality, management and human subjects research ethics before the training of data collectors is performed in Pakistan.

After the instruments have been pilot tested and vetted, AKU research staff will identify women who: 1) meet age, marital status and new DMPA user criteria, 2) independently present at the study site or are accompanied by an LHW, and 3) express a desire to use injectable contraception. AKU research staff will approach women at each study site, inviting those who self-identify as potential DMPA clients and meet eligibility criteria to participate in the trial. In low volume health facilities, all women will be approached; in a high-volume facility, such as a hospital, we will approach women based on a random number generator (e.g., every nth woman) to meet the desired sample size at each study site.

This study involves the provision of Sayana Press®, the subcutaneous form of DMPA that would not otherwise be available outside the study context, but only women who voluntarily and independently accept injectable contraception **before** study recruitment and enrolment will be asked to participate in this trial.

The trained RA posted at each study site will confirm eligibility to participate in the study and obtain consent. The RA will explain to potential participants that participation in the study involves being randomized to receive services from an LHV or an LHW and either DMPA IM or SP; being observed during service delivery at the facility; and being interviewed right after completing her visit at the facility. Thus, the RA will obtain consent for the following:

- Willingness to be randomized to provider and DMPA type
- Observation of screening and counseling for DMPA (identical procedure for IM and SP);
- Observation of first-time administration of either DMPA IM or SP (disparate procedures for the two);
- Exit interview right after she receives very first dose of DMPA and before she leaves the health facility.

With regard to providers, all LHVs will be interviewed, but only LHWs who provide DMPA services to at least nine new DMPA clients will be interviewed by RAs. With a 3:1 ratio of LHWs to LHVs, LHWs placed on rotation during the data collection period with approximately 34 clients being randomly assigned to LHWs per facilitya, it is possible that not all three LHWs participating in the trial will interact with at least nine DMPA clients. The threshold of nine DMPA clients served will ensure that LHWs interviewed obtain sufficient experience to share their perspectives on providing DMPA to new users. In order to interview some LHWs from rural sites, the quota will be lowered to include those who provided services to at least four new DMPA clients.

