### *LHW/LHV interview*

About four to six months after trial initiation, some participating LHWs and all LHVs will be asked for their permission (via informed consent) to be interviewed by an RA. By that time, they would have all provided initial and follow-up injections to their DMPA clients and should be able to describe their experiences. LHVs and LHWs will be interviewed at their assigned study sites.

As part of the interview process for LHWs only, the RA will be asked in advance of the meeting to bring their DMPA client materials with them. The RA will examine DMPA client records to verify that injection and re-injection dates are being recorded appropriately. Thus, as one of the objectives of the study, we will ascertain whether or not LHWs diligently record the dates of service for DMPA clients, how many are first-time or repeat DMPA clients, and if re-injection dates were scheduled for all of them. For LHWs who do not bring their logbook with them to the interview, a second and final session will be scheduled to capture that information. No additional attempts will be made to gather that information from the LHW and the data will be considered missing for that LHW.

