NO	13. Did you have a baby less than 6 months ago, are you fully or nearly-fully breastfeeding, and have you had no menstrual period since then?	YES
NO	14. Have you had a miscarriage or abortion in the last 7 days?	YES

Please record the action taken by the provider based on the client's responses:

Figure 3: Timeline of trial activities

Study Tasks	Month 1	Month 2	Month 3	Month 4	Month 5	Month 6	Month 7	Month 8	Month 9	Month 10	Month 11	Month 12
In-house review of study materials	X											
IRB (PHSC, AKU) review of study materials	X	X										
Local IRB(s) review of study materials		X	X									
SOW finalized with AKU			X									
Study prep in field (local approvals, community engagement)			X	X								
Orient trained LHV, select trained LHWs for rotation at study sites;				X								
Train RAs; conduct pilot tests				X								
Pilot-test trial procedures at study sites				X								
Recruit DMPA clients; conduct observations, exit interviews				X	X							
Conduct interviews with LHV and select LHWs									X	X		
Perform ongoing data entry, management and cleaning				X	X	X	X	X	X	X		
Analyze and interpret data								X	X	X		
Write-up trial results										X	X	
Disseminate trial results (in-country seminar, research brief, publications)											X	X

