IRBNET# 1035709: A randomized controlled trial of safety and effectiveness of Depo Provera intramuscular and subcutaneous administration comparing lay Lady Health Workers with clinically-trained Lady Health Visitors in Pakistan

STATISTICAL ANALYSIS PLAN

This statistical analysis plan gives a detailed explanation of the data analysis summary included in the study protocol.

I. Study Objectives

The goal of this evaluation is to assess whether the community health worker cadre, Lady Health Workers (LHWs) in Pakistan can screen and initiate women on intramuscular (IM) and subcutaneous Depo Provera injections as safely and effectively as their clinically-trained counterparts, Lady Health Visitors (LHV). Although LHWs are already allowed to provide follow-up doses in the community, this RCT will focus on the comparison of safety and effectiveness of screening, counseling and administration of DMPA IM and the subcutaneous injection, Sayana Press® (SP).

The study's primary outcomes are:

- Proportion of Lady Health Workers and Lady Health Visitors that appropriately screen women for DMPA use;
- Proportion of Lady Health Worker and Lady Health Visitor clients that report discussion with their respective providers on side effects, danger signs, advantages and disadvantages of DMPA use;
- Proportion of Lady Health Workers and Lady Health Visitors that demonstrate appropriate injection technique
- Proportion of Lady Health Workers and Lady Health Visitors that report needle stick injuries;
- Proportion of Lady Health Workers that properly maintains a client (re)injection log.

A secondary objective is to assess whether the clients of LHWs and LHV are equally satisfied with their respective providers and the family planning services they provide.

The study's secondary outcomes are:

- Satisfaction with the method;
- Satisfaction with the services received from the provider;
- Reports of client ability to speak freely and ask questions of provider;
- Friendly and respectful behavior toward client.

II. Study Design

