4. Interaction with and information provided by LHW/LHV about DMPA
5. Satisfaction with her choice of DMPA as a contraceptive method (IM or SP)
6. Satisfaction with LHW/LHV

A.2 LHW/LHV interview

Questionnaire items in the LHW/LHV interview instrument include:

- Sociodemographic characteristics
- Knowledge of DMPA use and provision
- Comparisons between the properties/characteristics of SP and DMPA IM injections
- General experiences and satisfaction with providing DMPA services
- Reports of needlestick injuries
- Observations of LHW (re)-injection logs

A.3 Observation Checklists

Three checklists adapted from existing instruments will be used to capture information on LHW and LHV services from the point of view of the observer. These are the source of the study's primary outcome measures for appropriate screening and counseling as well as appropriate injection technique.

The first checklist will adapt the 15 screening items from FHI 360’s “Checklist for Screening Clients Who Want to Initiate DMPA” (Figure 1). In addition, items that capture the presence or absence of counseling on DMPA use will be incorporated as a second part of this checklist instrument, such as:

- Discussion of advantages and disadvantages of DMPA use
- Warning or danger signs of DMPA use
- Side effects and management of DMPA

The remaining two checklists separately assess LHW and LHV injection technique for DMPA IM and SP. The content of the checklists was adapted from instruments developed for previous task sharing studies of injectable contraception and from PATH’s Sayana Press® training materials.

B. Data Management

A trained RA will be posted at each study site to conduct observations of the screening and counseling interaction between the LHW/LHV and client, and to conduct a brief interview with the client before she leaves the health facility (i.e., the client exit interview). Nurses at each health facility will serve as the gold standard to which LHW and LHV screening will be compared. That is, screening outcomes are considered accurate and appropriate if they agree with the gold standard nurse’s assessment immediately following the LHV’s or LHW’s screening of DMPA acceptors. About four to six months after trial initiation, all participating LHWs and LHVs will be asked for their permission (via informed consent) to be interviewed by an RA at their assigned study sites. All data will be recorded via pen and paper and later entered into an electronic database.

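### Protocol and SAP disagree on which LHWs are interviewed, so two listed primary outcomes could rest on a subset of LHWs selected by client volume

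*Protocol*

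**What the plan says.** **Protocol.** Under Pilot testing and recruitment procedures, all LHVs are interviewed, but "only LHWs who provide DMPA services to at least nine new DMPA clients will be interviewed by RAs". For rural sites, "the quota will be lowered to include those who provided services to at least four new DMPA clients". The stated reason is that interviewed LHWs should have enough experience to give a view on serving new users. The LHW/LHV interview section agrees: "some participating LHWs and all LHVs will be asked for their permission (via informed consent) to be interviewed by an RA". So does the Figure 3 timeline: "Conduct interviews with LHV and select LHWs".

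**SAP.** Section V.B (Data Management) says that "all participating LHWs and LHVs will be asked for their permission (via informed consent) to be interviewed by an RA at their assigned study sites". It mentions no client threshold.

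**Outcomes that depend on the interview.** SAP section I lists among the primary outcomes "Proportion of Lady Health Workers and Lady Health Visitors that report needle stick injuries", and also the proportion of LHWs who keep a proper (re)injection log. SAP Table 2 names the LHW/LHV questionnaire as the source for both, and the Protocol's Questionnaires section places both in that instrument. Needle-stick injuries are stratified by cadre. The log outcome is defined, examined and tabulated for LHWs only. Under Data Cleaning, the SAP drops missing values from the denominator of proportions.

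**The concern.** An LHW who is not interviewed has no data on either outcome. Because missing values leave the denominator, she need not appear in the reported proportion at all. Under the Protocol rule, whether an LHW is measured depends on how many trial clients she served, while every LHV is measured. The needle-stick comparison would then set a filtered group beside an unfiltered one. The log result would describe only the busier LHWs. The urban and rural LHW columns of SAP table shell 4 would also rest on different entry rules.

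The Protocol's reason for the threshold suits questions about experience and opinion. It does not explain why an LHW with few clients should not be asked about an injury or have her log checked. Needle-stick injury is a provider-safety measure in a trial whose objective is to show that LHWs initiate DMPA as safely as LHVs. With 30 LHWs at most, each one left out matters to a simple proportion.

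There is also a practical problem: field staff following the Protocol and analysts following the SAP would be working to different rules.

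**Working it through.** **Inputs**
- Urban clients: 342 over 5 sites (Protocol, Sample size and footnote a).
- Rural clients: "expect to enroll approximately 100 DMPA acceptors from the rural facilities in the recruitment period", over 5 sites.
- Allocation 1:1 between cadres; three LHWs and one LHV per site (Protocol, Sample size).
- 30 LHWs and 10 LHVs (SAP Table 1), so 15 urban and 15 rural LHWs.
- Thresholds: nine urban, four rural. I read them as counts of trial clients, because the Protocol sets the nine beside its figure of about 34 LHW clients per facility.
- Rotation follows when each LHW is available. No shares are given, so every share below is an assumption.

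**The plan's own figure.** 342 / 5 / 2 = 34.2 LHW clients per urban site, against about 34 stated. It reproduces.

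**Mean clients per LHW.** Urban: 34 / 3 = 11.3, above nine. Rural: 100 / 5 / 2 = 10 per site, and 10 / 3 = 3.3, below four.

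**A limit that needs no share assumption.** Three rural LHWs reaching four each need 3 × 4 = 12 clients. With exactly 10, at most two can qualify, so at least one per site (5 of 15) is left out. If the LHW share of 20 rural clients instead varies at random around 10, and clients fall equally on the three LHWs, all three reach four at only about 4% of sites.

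**Equal and independent allocation.** One LHW's count is binomial with probability 1/3.
- Urban: P(X ≥ 9 | n = 34) = 0.849. Expected left out: 15 × (1 − 0.849) = 2.3.
- Rural: P(X ≥ 4 | n = 10) = 0.441. Expected left out: 15 × (1 − 0.441) = 8.4.
- Total: 2.3 + 8.4 = 10.7, about 11 of 30.
- All three LHWs at an urban site reach nine with probability 0.56.

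**Other assumed rotations** (multinomial simulation, except the strictly even row)

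| Shares | Urban qualifying, of 15 | Rural qualifying, of 15 | Left out, of 30 |
|---|---|---|---|
| Strictly even (12/11/11 and 4/3/3) | 15 | 5 | 10 |
| Equal, random | 12.7 | 6.6 | 10.7 |
| 50/30/20 | 9.8 | 6.5 | 13.7 |
| 60/20/20 | 7.3 | 5.9 | 16.8 |

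In every row no LHV is left out. Under the SAP rule no LHW is left out either.

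**Direction of bias.** The outcome is whether a provider reports any injury, which should rise with the number of injections given. Take 1% per injection as an illustration only. The chance of at least one injury is 1 − 0.99^34 = 29% at 34 clients (an urban LHV), about 10% at 11 (the urban LHW mean) and 3% at three. Dropping low-volume LHWs removes those with least exposure, which pushes the LHW proportion up. It also removes those with least practice, which pushes it down. The documents do not say which effect is larger.

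**The case against.** The strongest reply is that little turns on this. Both outcomes are descriptive in the SAP, with no test or margin. The powered outcome, screening, is observed for each client and does not use the interview. Most of the LHWs left out are rural, a group the Protocol already calls too small for separate analysis. If the data are not pooled, the focus is on urban sites, where the expected loss is about 2 of 15 under equal random allocation and nil under strictly even rotation. The Protocol also discloses that not every LHW may reach nine. All of this stands and limits the importance of the point. It does not remove the contradiction, or the lack of a reason for filtering injury and log data.

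A reader might infer more than the documents support:
- **That the threshold flatters LHWs.** The exposure argument can run the other way, so no direction can be claimed.
- **That LHWs drop out after an injury or poor performance.** No such link is documented. Rotation is said not to depend on perceived competence, and providers are not penalized for shortcomings.
- **That both outcomes compare filtered LHWs with unfiltered LHVs.** The log has no LHV arm. The unequal comparison applies to needle-stick injuries only.
- **That the rural cut-off contradicts the planning figures.** The Protocol lowers it so that some rural LHWs are interviewed. A mean of 3.3 is compatible with some reaching four, and rural sites are chosen to enrol 20 or more.

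Interviewing everyone also leaves the larger comparability problem in place: an urban LHV serves about 34 trial clients and an urban LHW about 11.

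**Conclusion.** The contradiction is real and lies in the current text of both documents. If the Protocol rule is followed, needle-stick injuries are compared between a volume-selected subset of LHWs and all LHVs, and log upkeep is described in that subset alone. The expected loss is about 11 of 30 LHWs (about 8 rural, 2 urban) against 0 of 10 LHVs, assuming equal and independent allocation and 10 LHW clients per rural site. It is about 10 with strictly even rotation and about 14 to 17 with the uneven shares tried. If the SAP rule is followed the loss is zero. The size is therefore conditional, and the direction of bias is undetermined. This does not threaten the main non-inferiority result. It should be settled because it concerns a listed safety outcome and is cheap to correct.

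**What to change.** - Amend the Protocol in three places (the provider-interview paragraph under Pilot testing and recruitment procedures, the LHW/LHV interview section, and the Figure 3 timeline) so that they match the SAP for the needle-stick and log items. Every LHW who served at least one trial client is asked about injuries and has her log checked, including any who left the rotation.
- Keep a client threshold, if one is wanted, for opinion and experience items only, and state it in the SAP as well.
- Report both outcomes with the number of participating LHWs and the number interviewed; give the same counts for LHVs on needle-stick injuries.
- Report trial injections per provider beside the needle-stick result, so that unequal exposure is visible.

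The cost is a wording amendment and, on the rotations assumed above, roughly 11 to 17 more short interviews or log checks by research assistants already at the sites.
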